## 2.2 CTEP IND Agent

### 2.2.1 Nivolumab

Nivolumab targets the programmed death-1 (PD-1, cluster of differentiation 279 [CD279]) cell surface membrane receptor. PD-1 is a negative regulatory receptor expressed by activated T and B lymphocytes. Binding of PD-1 to its ligands, programmed death-ligand 1 (PD-L1) and 2 (PD-L2), results in the down-regulation of lymphocyte activation. Nivolumab inhibits the binding of PD-1 to PD-L1 and PD-L2. Inhibition of the interaction between PD-1 and its ligands promotes immune responses and antigen-specific T-cell responses to both foreign antigens as well as self-antigens.

The indirect drug-drug interaction potential of nivolumab was assessed using systemic cytokine modulation data for cytokines known to modulate CYP enzymes. There were no meaningful changes in cytokines known to have indirect effects on CYP enzymes across all dose levels of nivolumab. This lack of cytokine modulation suggests that nivolumab has no or low potential for modulating CYP enzymes, thereby indicating a low risk of therapeutic protein-drug interaction.

Adverse events (AEs) associated with Nivolumab exposure may represent an immunologic etiology. These AEs may occur shortly after the first dose or several months after the last dose of treatment. Nivolumab must be withheld for drug-related toxicities and severe or life-threatening AES and prednisone may be given.

The proposed dosing of nivolumab is 240 mg every 2 weeks starting on Day 14 of cycle 1. This is the package insert dosing scheme used when nivolumab is combined with other agents (namely, ipilimumab). We will be combining nivolumab with two other agents, therefore this is consistent with current practice. Weight based dosing will allow us to mitigate adverse events, especially when combined with other agents.

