Antibody drug clearance has been demonstrated as an early biomarker for outcomes from immune checkpoint inhibitor therapy in some disease populations [32037060, 32089494]. In particular, baseline clearance (CL0, the clearance of the first dose of antibody drug) and/or changes in clearance over time significantly associate with PFS and/or overall survival (OS) for CTLA4-targeted [31709718], PD1-targeted [28573468, 28182273, 29891725, 30018117, 31710163, 761097Orig1s000], and PDL1-targeted agents [30980481, 29243223] (low baseline clearance and decreasing clearance over time correlates with better outcomes). Sex is also a significant covariate for nivolumab clearance in patients with advanced solid tumors [PMC6767401, PMC5270302]. Elevated baseline clearance is also observed in patients with cancer-associated cachexia, and decreasing clearance over time trends with weight gain in patients who are responding to therapy. It is not currently known if CL0 or change in CL over time for nivolumab will serve as a predictive biomarker in this patient population, so we aim to evaluate this within the trial.

Integration of venetoclax, decitabine, and nivolumab PK/PD will allow assessment of exposure-response relationships.

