## 5. BIOMARKER, CORRELATIVE, AND SPECIAL STUDIES

### 5.1 Summary Table for Specimen Collection

Time Point	Specimen	Send Specimens To:
Baseline		
Pre-venetoclax/azole	
 
4 mL Peripheral Blood (EDTA-containing vacutainer) – OATP1B1 plasma biomarker
 
	OSU PharmacoAnalytical Shared Resource for ChOP-KC
	
 
10 mL of bone marrow aspirate in sodium heparin tubes (mandatory)
 
15 mL blood in ACD tubes (mandatory)
 
	Ohio State Leukemia Tissue Bank
	
 
Correlatives: Flow cytometry, Cytogenetics, Next-generation sequencing, Tetramer Analysis, and DNA methylation
 
	
Cycle 1 Day 14 (C1D14)		
Pre-venetoclax, 1h, 2, 4, 7h, 24h	
 
4 mL Peripheral Blood (EDTA-containing vacutainer) – Venetoclax plasma levels, OATP1B1 plasma biomarker assay
 
	OSU PharmacoAnalytical Shared Resource for ChOP-KC
Pre-nivolumab, 4h after end of infusion	
 
3 mL Peripheral Blood (red top vacutainer) – Nivolumab serum levels
 
	
Day 28 +/- 1 day of cycles 1, 2, and 3		
	
 
10 mL of bone marrow aspirate in sodium heparin tubes (mandatory)
 
15 mL blood in ACD tubes (mandatory)
 
	Ohio State Leukemia Tissue Bank
	
 
Correlatives: Flow cytometry, Cytogenetics, Next-generation sequencing, Tetramer Analysis, and DNA methylation
 
	
Day 28 +/- 1 day every 3 cycles starting with cycle 6 (ex. Cycles 6, 9, 12...)		
	
 
10 mL of bone marrow aspirate in sodium heparin tubes (mandatory)
 
15 mL blood in ACD tubes (mandatory)
 
	Ohio State Leukemia Tissue Bank
	
 
Correlatives: Flow cytometry, Cytogenetics, Next-generation sequencing, Tetramer Analysis, and DNA methylation
 
	
Day 28 +/- 1 day of end of every cycle starting with cycle 4 (excluding cycles 6, 9, 12... as above)		
	
 
10 mL blood in ACD tubes (mandatory)
 
	Ohio State Leukemia Tissue Bank
	
 
Correlatives: DNA methylation
 
	
Induction Cycle 2 Day 1		

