Pre-nivolumab, 4h after end of infusion	3 mL Peripheral Blood (red top vacutainer) – Nivolumab serum levels	OSU PharmacoAnalytical Shared Resource for ChOP-KC
Maintenance Cycle 1 (Day 1)		
Pre-nivolumab, 4h after end of infusion	3 mL Peripheral Blood (red top vacutainer) – Nivolumab serum levels	OSU PharmacoAnalytical Shared Resource for ChOP-KC
Maintenance Cycle 3 (Day 14)		
Pre-nivolumab, 30 min after end of infusion	3 mL Peripheral Blood (red top vacutainer) – Nivolumab serum levels	OSU PharmacoAnalytical Shared Resource for ChOP-KC
End of Treatment/Relapse		
	

• 10 mL of bone marrow aspirate in sodium heparin tubes (mandatory)

• 15 mL blood in ACD tubes (mandatory)

 

• Correlatives: Flow cytometry, Cytogenetics, Next-generation sequencing, Tetramer Analysis, and DNA methylation

	Ohio State Leukemia Tissue Bank
~ 2 weeks after last nivolumab infusion	

• 3 mL Peripheral Blood (red top vacutainer) – Nivolumab serum levels

	OSU PharmacoAnalytical Shared Resource for ChOP-KC

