## 6. TREATMENT PLAN

### 6.1 Agent Administration

Treatment will be administered as either an outpatient or inpatient basis as appropriate. Reported adverse events and potential risks are described in Section 10. Appropriate dose modifications are described in Section 7. No investigational or commercial agents or therapies other than those described below may be administered with the intent to treat the patient's malignancy.

Dose Scheduling			
Dose level	Venetoclax*	Decitabine	Nivolumab
Dose level -2	Cycle 1 Day 1 100mg Cycle 1 Day 2 200mg Cycle 1 Day 3-14 400mg  Cycle 2 and beyond Day 1-14 400mg	Induction 20 mg/m  intravenously on Days 1-10  Maintenance 20 mg/m  intravenously on Days 1-5	Flat dose of 240mg every 2 weeks starting on Day 15 of Cycle 1 and continue Day 1 and 15 with cycle 2 and subsequent cycles
Dose level -1	Cycle 1 Day 1 100mg Cycle 1 Day 2 200mg Cycle 1 Day 3-21 400mg  Cycle 2 and beyond Day 1-21 400mg		
Dose level 1	Cycle 1 Day 1 100mg Cycle 1 Day 2 200mg Cycle 1 Day 3-28 400mg  Cycle 2 and Cycle 3 (if needed) Day 1-28 400 mg  Maintenance cycles Day 1-21 400 mg		

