## 11. STUDY CALENDAR

Baseline evaluations are to be conducted within 10 days prior to start of protocol therapy. In the event that the patient's condition is deteriorating, laboratory evaluations should be repeated within 48 hours prior to initiation of the next cycle of therapy.

	Pre-Study	Induction cycle 1	Induction cycles 2-3 (If needed)	Maintenance cycles	Relapse/Off Study
Decitabine		D	D	D	
Nivolumab		N	N	N	
Venetoclax		V	V	V	
Informed consent	X				
Demographics	X				
Medical history	X				
Concurrent meds a	X	X	X	X	
Physical exam b	X	X	X	X	X
Vital signs c	X	X			X
Height	X				
Weight	X	X			X
Performance status d	X	X			X
Serum Chemistry e	X	X	X	X	X
CBC w/diff f	X	X	X	X	X
EKG	X				
Adverse event evaluation g	X	X	X	X	X
Pregnancy test h	X	X	X	X	
Bone marrow i	X	X	X	X	X
Correlative studies j	X	X	X	X	X

D: Decitabine will be given on Days 1-10 of Induction cycles and Days 1-5 of maintenance cycles

N: Nivolumab will be given on Day 15 of cycle 1 and Days 1 and 15 of all subsequent cycles

V: Venetoclax will be given on Days 1-28 of induction cycles and Days 1-21 of maintenance cycles. Dosing ramp-up on days 1-3 or 1-4 (based on concurrent use of CYP3A inhibitors as outlined in Section 6.3.1)

a: Concurrent medications should be assessed at screening and the beginning of each treatment cycle

b: Physical exam should be performed at Screening, Days 1 and 15 of every cycle and End of Treatment/Relapse

c: Vital signs should be performed at Screening, Days 1 and 15 of every cycle and End of Treatment/Relapse. Vitals signs include blood pressure, heart rate, temperature, oxygen saturation, and respiratory rate.

d: Performance status should be evaluated at Screening, Day 1 of each cycle of therapy, and End of Treatment/Relapse

e: Serum chemistry will include: Na, K, CO2, Cl, BUN, Cr, AST, ALT, AP, TB, TP, albumin, LDH, and uric acid should be performed at screening, pre-dose (within 4 hours prior to venetoclax administration), every 12 hours during venetoclax ramp-up period (see Appendix C for tumor lysis management guidelines), twice weekly otherwise during induction cycles and at the beginning of each maintenance cycle and relapse/EOT

f: CBC with differential. To be performed at screening, twice weekly during induction cycles, and at the beginning of each maintenance cycle and relapse/EOT.

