### 1.2 Nivolumab Serum Pharmacokinetic Samples

- The plasma pharmacokinetic profile of nivolumab will be characterized by collecting blood samples (as outlined in the Study Calendar and in the separate PK study worksheet uploaded at the Cancer Trials Support Unit website [www.ctsu.org](http://www.ctsu.org)).

- Collection of Specimen(s): patients will have 3 mL samples of blood collected in tubes containing heparin as an anticoagulant (red top) at the time points specified below:

- **Cycle 1 Day 14**
  - **Pre-nivolumab infusion**
    - 4h after end of nivolumab infusion
- **Induction Cycle 2 Day 1**
  - **Pre-nivolumab infusion**
    - 4h after end of nivolumab infusion
- **Maintenance Cycle 1 (Day 1)**
  - **Pre-nivolumab infusion**
    - 4h after end of nivolumab infusion
- **Maintenance Cycle 3 (Day 14)**
  - **Pre-nivolumab infusion**
    - 4h after end of nivolumab infusion
- **End of Treatment/Relapse**
  - ~ 2 weeks after last nivolumab infusion
  - Obtain venous blood by standard phlebotomy technique from a peripheral access point. NOTE: Suggest using a minimum 18G needle to avoid sample hemolysis.
    - Obtain venous blood by standard phlebotomy technique from a peripheral access point.
  - Fill-up the tubes as much as possible until blood flow stops.
  - GENTLY invert each tube several times (8-10 times) immediately after collection and then allow blood to clot for 30-60 minutes at room temperature before centrifugation.

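### Infusion-timed nivolumab PK draws are labelled Day 14 at Cycle 1 and Maintenance Cycle 3, but the treatment sections infuse on Day 15, so two of nine draws cannot be taken on the stated day

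*Combined protocol and SAP*

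**What the plan says.** **Sampling.** Section 5.1 has a block headed "Cycle 1 Day 14 (C1D14". It holds the venetoclax profile and a nivolumab pair specified as "Pre-nivolumab, 4h after end of infusion". Appendix F, part 1.2, gives the same day and times. Both documents add a second mid-cycle pair, shown in Appendix F as "Maintenance Cycle 3 (Day 14"). For that pair Section 5.1 asks for "Pre-nivolumab, 30 min after end of infusion", whereas Appendix F asks for 4 h.

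**Dosing.** Section 6.1 gives "Flat dose of 240mg every 2 weeks starting on Day 15 of Cycle 1". The study calendar in Section 11 says "Nivolumab will be given on Day 15 of cycle 1 and Days 1 and 15 of all subsequent cycles". The schema and the regimen table agree, and Section 6.3 starts the DLT window with nivolumab on C1D15. For doses missed or delayed for reasons other than toxicity, Section 7.5 allows up to two days later and no earlier window.

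**Exceptions.** Background Section 2.2.1 says "240 mg every 2 weeks starting on Day 14 of cycle 1". The PK entries of the biomarker plan in Section 5.6 give Day 14/15 for Cycle 1 and Day 14 for Maintenance Cycle 3.

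**Purpose.** PK and PD form secondary objective 1.2.8. Section 2.5.4 singles out "baseline clearance (CL0, the clearance of the first dose of antibody drug") and its change over time as candidate predictors of outcome. Section 9.3 plans non-compartmental analysis followed by population modelling, with clearance and volume among the parameters.

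**The concern.** A draw defined by the end of an infusion has no meaning on a day without one. Sites that read the day label may resolve this differently: some will move the pair to the infusion day, some may take only the pre-infusion sample on Day 14. A first-dose post-infusion sample that is missed cannot be recovered.

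The text offers little to settle the matter. Appendix F refers sites to the study calendar, but its correlative table (Section 11.1) lists no PK draws, and calendar footnote j points back to Sections 5.1 and 11.1. The calendar's examination, vital-sign and adverse-event visits fall on Days 1 and 15.

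At Maintenance Cycle 3, the last scheduled on-treatment occasion and so one that informs change in clearance, sites also have two different post-infusion times to choose from.

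**Working it through.** The plan gives no figure to reproduce. The check sets sampling days against dosing days and counts.

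**1. Occasions and draws** (Section 5.1 and Appendix F against the schema and Sections 6.1 and 11)

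| Occasion | Sampling day | Draws | Infusion day in treatment sections | Match |
|---|---|---|---|---|
| Cycle 1 | 14 | 2 | 15 | no |
| Induction Cycle 2 | 1 | 2 | 1 and 15 | yes |
| Maintenance Cycle 1 | 1 | 2 | 1 and 15 | yes |
| Maintenance Cycle 3 | 14 | 2 | 1 and 15 | no |
| End of treatment/relapse | about 2 weeks after last dose | 1 | none | yes |

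Total: 2 + 2 + 2 + 2 + 1 = 9 draws. Four carry a Day 14 label. The two pre-infusion draws among them would still precede the dose on Day 14. The two post-infusion draws are impossible that day. So 2 of 9 are affected, or 2 of 7 for a patient who responds in Cycle 1 and skips induction Cycle 2 (9 − 2 = 7). A patient who never reaches maintenance has 2 + 2 + 1 = 5 draws if Cycle 2 is given, with 1 affected.

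**2. Day arithmetic.** With Cycle 1 infusion on Day 15, or up to two days later, it falls on Days 15 to 17. Day 14 is then 15 − 14 = 1 to 17 − 14 = 3 days before the first dose. In Maintenance Cycle 3, on schedule, Day 14 is 14 − 1 = 13 days after one dose and 1 day before the next.

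**3. Does Section 2.2.1 remove the conflict?** If Cycle 1 infusion were on Day 14, the Cycle 1 label would be right. Carrying a strict two-week interval forward in 28-day cycles gives Days 14 and 28 (14 + 14 = 28). That fits the Maintenance Cycle 3 label but breaks the two Day 1 labels. Infusions on Days 1 and 14 would fit all four labels, but no section states that pattern, and its intervals would alternate between 13 days (14 − 1) and 15 days (29 − 14). No dosing schedule written in the documents agrees with every sampling label.

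**4. What the first post-infusion sample contributes.** Before the second dose, the schedule yields two samples containing drug: the 4 h sample and the next pre-dose trough. As an illustration, assume one compartment, C(t) = (Dose/V) × exp(−(CL/V) × t). Two concentrations give CL/V = ln(C1/C2)/(t2 − t1), and V then follows from C1. The trough alone is one equation in two unknowns. So for one patient's first dose, losing the 4 h sample means CL and V cannot be separated without information from elsewhere.

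**The case against.** The strongest reply is that every draw is already specified relative to the infusion. An attentive site would follow the infusion and ignore the day heading, and Section 5.6's Day 14/15 can be read as Day 14 for venetoclax and Day 15 for nivolumab. Appendix F also cites a separate PK worksheet, which is not among the documents and may be correct. All of this stands, and it means that actual loss of samples is a risk, not a demonstrated outcome. It does not remove the contradiction, and at Maintenance Cycle 3 Section 5.6 repeats Day 14.

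A reader might infer that CL0 could not be estimated. The documents do not support that. Section 9.3 plans a population model, in which post-infusion samples at induction Cycle 2 and Maintenance Cycle 1 also inform volume. The cost would be precision.

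A reader might also infer that two whole occasions are lost, or that Maintenance Cycle 3 values could not be compared. Only the post-infusion draws are impossible on Day 14. Appendix F requires the draw time on each vial, and a PK model can use actual times.

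Finally, Appendix F tells sites to label PK vials #10417, although this trial is 10317. Specimen mix-up might be inferred, but Section 5.3.2.1 requires patient and specimen identifiers and Appendix F asks for the study number and a PK form or sample list with each shipment. It is a minor label error.

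**Conclusion.** The sampling days and the operative dosing days contradict each other at two of the four on-treatment nivolumab PK occasions. With infusion on Day 15, two of nine scheduled draws cannot be taken on the stated day. The Maintenance Cycle 3 post-infusion time is a second contradiction, 30 min against 4 h.

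The consequence is a risk to the precision of first-dose clearance if sites follow the day label. Its size cannot be computed, because the documents give no variance components and no expected rate of missed samples. The count assumes a full course with induction Cycle 2 and at least three maintenance cycles, and that the unseen worksheet does not override the protocol. Section 5.6 classes these assays as exploratory, although they serve a stated secondary objective. No DLT, MTD or response decision depends on them. This is a wording correction that should be made because the samples cannot be recovered afterwards.

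**What to change.** - In Sections 5.1 and 5.6 and Appendix F, replace the Day 14 label on the nivolumab draws with the day of the nivolumab infusion: the first infusion for Cycle 1, and the mid-cycle infusion for Maintenance Cycle 3. Ask for actual clock times of end of infusion and of each draw.
- State one post-infusion time for Maintenance Cycle 3 in both Section 5.1 and Appendix F. Using 4 h would match the other on-treatment occasions.
- Leave the Cycle 1 venetoclax profile on Day 14. Its 24 h sample falls on Day 15.
- Reconcile Section 2.2.1 with Section 6.1 on the nivolumab start day. This review takes no position on which is right.
- Correct #10417 to 10317 in Appendix F, parts 1.1.1 and 1.2.1, and check the PK worksheet against the revised text.

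The cost is table and appendix wording and, if needed, a revised worksheet. No samples or visits are added.

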## 5.2 Specimen Procurement Kits and Scheduling

### 5.2.1 Specimen Procurement Kits

Institutional supplies should be used for shipping specimens.

### 5.2.2 Scheduling of Specimen Collections

Please adhere to the following guidelines when scheduling procedures to collect tissue:

- Bone marrow aspirates collected must be sent to the corresponding lab on the same day of collection. Bone marrow aspirate can be collected Monday through Friday
- Fresh blood specimens may be collected and sent Monday through Friday.

## 5.3 Specimen Tracking System Instructions

### 5.3.1 Specimen Tracking System Overview and Enrollment Instructions

For the ETCTN STS, the following information will be requested:

- Protocol Number
- Investigator Identification
  - Institution and affiliate name
  - Investigator's name
- Eligibility Verification: Patients must meet all the eligibility requirements listed in Section 3.
- Additional Requirements:
  - Patients must provide a signed and dated, written informed consent form.

Upon enrolling a patient, IWRS will communicate with OPEN, assigning two separate and unique identification numbers to the patient, a Universal patient ID (UPID) and a Treatment patient ID. The UPID is associated with the patient and used each and every time the patient engages with the portion of this protocol that uses the ETCTN Specimen Tracking System. The UPID contains no information or link to the treatment protocol. IWRS will maintain an association between the UPID for ETCTN biobanking and molecular characterization and any treatment protocols the patient participates in, thereby allowing analysis of the molecular characterization results with the clinical data.

Immediately following enrollment, the institutional anatomical pathology report for the diagnosis under which the patient is being enrolled must be uploaded into Rave. The report must include the surgical pathology ID (SPID), collection date, block number, and the IWRS-assigned UPID and patient study ID for this trial. For newly acquired biopsies, the radiology and operative report(s) must also be uploaded into Rave. **Important: Remove any personally identifying information, including, but not limited to, the patient's name, initials, medical record number, and patient contact information from the institutional pathology report prior to submission.**

Additionally, please note that the STS software creates pop-up windows when reports are generated, so you will need to enable pop-ups within your web browser while using the software.

For questions regarding the Specimen Tracking System, please contact the Theradex Help Desk at [[contact]](mailto:[contact]).

A shipping manifest **must** be included with all sample submissions.

### 5.3.2 Specimen Labeling

#### 5.3.2.1 Blood Specimen Labels

Include the following on blood specimens (including whole blood and frozen, processed blood products – like serum and plasma):

- Patient Study ID
- Universal Patient ID (UPID)
- Specimen ID (automatically generated by Rave)
- Time point
- Specimen type (*e.g.*, blood, serum)
- Collection date (to be added by hand)

[figure not shown]
#### 5.3.2.2 Tissue Specimen Labels |

Include the following on all tissue specimens or containers (*e.g.*, formalin jar):

- Patient Study ID
- Universal Patient ID (UPID)
- Specimen ID (automatically generated by Rave)
- Time point
- Specimen type (*e.g.*, formalin-fixed paraffin-embedded [FFPE] Block, Formalin Fixed Tissue, Fresh Tissue in Media, *etc.*)
- Tissue type (P for primary, M for metastatic or N for normal)
- Surgical pathology ID (SPID) number
- Block number from the corresponding pathology report (archival only)
- Collection date (to be added by hand)

#### 5.3.2.3 Example of Specimen Label

The following image is an example of a tissue specimen label printed on a standard Avery label that is 1" high and 2.625" wide.

The QR code in the above example is for the Specimen ID shown on the second line.

**NOTE:** The QR code label is currently under development at Theradex as of 31-Aug-2018; therefore, labels generated by the STS for this study may not include a QR code.

The second line item from the end includes four data points joined together:

1. Tissue only: Primary (P), Metastatic (M), Normal (N) tissue indicated at the beginning of the specimen ID; this field is blank if not relevant (e.g., for blood)
2. Block ID or blank if not relevant
3. SPID (Surgical Pathology ID) or blank if none
4. The last alpha-numeric code is protocol specific and is only included if the protocol requires an additional special code classification

The last line on the example label is for the handwritten date and optional time.

### 5.3.3 Overview of Process at Treating Site

#### 5.3.3.1 OPEN Registration

All registrations will be performed using the Oncology Patient Enrollment Network (OPEN) system. OPEN communicates automatically with the Interactive Web Response System (IWRS) which handles identifier assignments, any study randomization, and any prescribed slot assignments. If specimen analysis is required to determine eligibility, the protocol will be setup with multi-step registration.

Registration with eligibility specimen analysis:

1. Site enters first step data into OPEN.
2. IWRS receives data from OPEN, generates the Patient Study ID and the Universal Patient ID, both of which are sent back to OPEN.
3. IWRS sends first step registration data, including the IDs and a TAC of "NOT REG" directly to Rave.
4. The specimen tracking system in Rave is utilized for the specimen that contributes to eligibility determination.
5. Site enters second and any subsequent step data into OPEN including results of specimen analysis.
6. IWRS receives all data from OPEN, then sends it onto Rave with either the treatment

TAC or a TAC of “SCRN FAIL”.

7. In addition to the specimen tracking forms completed to determine eligibility, data entry for screen failure patients should include Histology and Disease, all forms in the Baseline folder, any lab forms connected to eligibility determination, and Off Treatment/Off Study.

Any data entry errors made during enrollment should be corrected in Rave.

